1.4.1.3 Descriptive Endpoints – Randomized Cohort

The following descriptive endpoints will be assessed and reported:

- Technical Success at exit from procedure room: [REDACTED]
[REDACTED]
[REDACTED]
[REDACTED]
- Device Success at 30-day post-procedure: [REDACTED]
[REDACTED]
[REDACTED]
[REDACTED]
- Procedural Success at 30-day post-procedure: [REDACTED]
[REDACTED]
- Incidence of peripheral edema requiring hospitalization at 12 months, and annually through 24, 36, 48, and 60 months
- Incidence of ascites at 12 months, and annually through 24, 36, 48, and 60 months
- Incidence of IV diuretic administration (including outpatient clinics) at 12 months, and annually through 24, 36, 48, and 60 months
- Change in KCCQ score from baseline through 30 days, 6 months, 12 months and 24, 36, 48, and 60 months

Statistical Analysis Plan

- SF-36 QoL scores at baseline, 30 days, 12 months and 24 months (and change from baseline to follow-up)
- Change in NYHA Functional Class (III/IV to I/II) from baseline through 30 days, 6 months, 12 months and 24, 36, 48, and 60 months
- Change in 6MWT from baseline through 30 days, 6 months, 12 months and 24, 36, 48, and 60 months
- Change in BNP/NT-proBNP from baseline through 30 days, 6 months, 12 months, and annually through 24, 36, 48, and 60 months
- Change in gamma-GGT from baseline through 30 days, 6 months, 12 months, and annually through 24, 36, 48, and 60 months
- Change in patient weight from baseline through 30 days, 6 months, 12 months and 24, 36, 48, and 60 months
- Change in kidney function (assessed using eGFR) from baseline through 30 days, 6 months, 12 months and 24, 36, 48, and 60 months
- Change in liver function (assessed using the MELD score) from baseline through 30 days, 6 months, 12 months and 24, 36, 48, and 60 months
- Echocardiographic endpoints assessed from baseline through 30 days, 6 months, 12 months and 24, 36, 48, and 60 months post procedure, as follows:
 - TR severity grade
 - Tricuspid valve annulus diameter
 - Effective Regurgitant Orifice Area (EROA)
 - Regurgitant Volume
 - Vena Contracta Width
 - Right Ventricular End Diastolic Dimension (RVEDD)
 - Right Ventricular Fractional Area Change
 - Left Ventricular End Diastolic Volume (LVEDV)
 - Left Ventricular End Systolic Volume (LVESV)
 - Tricuspid Annular Plane Systolic Excursion (TAPSE)
 - Cardiac Output
 - Forward Stroke Volume (Left Ventricle)
 - Inferior Vena Cava Dimension

1.4.2 Endpoints – Single-arm Cohort

1.4.2.1 Primary Endpoint – Single-arm Cohort

Statistical Analysis Plan

The primary endpoint of the Single-arm cohort is survival at 12 months with a quality of life improvement (assessed using KCCQ overall score) of at least 10 points compared to baseline.

1.4.2.2 Secondary Endpoints – Single-arm Cohort

The following secondary endpoints will be assessed at the same time of the primary endpoint:

- TR Reduction by at least one grade at 30-day post procedure as compared to baseline.
- Freedom from MAE occurring after procedure attempt (femoral vein puncture) at 30 days.
Components of MAE consist of the following:
 - Cardiovascular Mortality,
 - New Onset Renal Failure,
 - Endocarditis Requiring Surgery, and
 - Non-Elective Cardiovascular Surgery for TriClip™ device-related AE post-index procedure.
- Change in 6MWT at 12 months, as compared to baseline
- Recurrent HF hospitalizations at 12 months compared to the rate of heart failure hospitalizations in the prior 12 months
- Freedom from all-cause mortality and tricuspid valve surgery at 12 months

1.4.2.3 Descriptive Endpoints – Single-arm Cohort

The following descriptive endpoints will be assessed and reported:

- Technical Success at exit from procedure room: [REDACTED]
[REDACTED]
[REDACTED]
[REDACTED]
- Device Success at 30-day post-procedure: [REDACTED]
[REDACTED]
[REDACTED]
[REDACTED]
- Procedural Success at 30-day post-procedure: [REDACTED]
[REDACTED]
- Incidence of peripheral edema requiring hospitalization at 12 months, and annually through 24, 36, 48, and 60 months
- Incidence of ascites at 12 months, and annually through 24, 36, 48, and 60 months
- Incidence of IV diuretic administration (including outpatient clinics) at 12 months, and annually through 24, 36, 48, and 60 months

Statistical Analysis Plan

- Change in KCCQ score from baseline through 30 days, 6 months, 12 months and 24, 36, 48, and 60 months
- SF-36 QoL scores at baseline, 30 days, 12 months and 24 months (and change from baseline to follow-up)
- Change in NYHA Functional Class (III/IV to I/II) from baseline through 30 days, 6 months, 12 months and 24, 36, 48, and 60 months
- Change in 6MWT from baseline through 30 days, 6 months, 12 months and 24, 36, 48, and 60 months
- Change in BNP/NT-proBNP from baseline through 30 days, 6 months, 12 months, and annually through 24, 36, 48, and 60 months
- Change in gamma-GGT from baseline through 30 days, 6 months, 12 months, and annually through 24, 36, 48, and 60 months
- Change in patient weight from baseline through 30 days, 6 months, 12 months and 24, 36, 48, and 60 months
- Change in kidney function (assessed using eGFR) from baseline through 30 days, 6 months, 12 months and 24, 36, 48, and 60 months
- Change in liver function (assessed using the MELD score) from baseline through 30 days, 6 months, 12 months and 24, 36, 48, and 60 months
- Echocardiographic endpoints assessed from baseline through 30 days, 6 months and 12 months post procedure, as follows:
 - TR severity grade
 - Tricuspid valve annulus diameter
 - Effective Regurgitant Orifice Area (EROA)
 - Regurgitant Volume
 - Vena Contracta Width
 - Right Ventricular End Diastolic Dimension (RVEDD)
 - Right Ventricular Fractional Area Change
 - Left Ventricular End Diastolic Volume (LVEDV)
 - Left Ventricular End Systolic Volume (LVESV)
 - Tricuspid Annular Plane Systolic Excursion (TAPSE)
 - Cardiac Output
 - Forward Stroke Volume (Left Ventricle)
 - Inferior Vena Cava Dimension

Statistical Analysis Plan

1.4.3 Descriptive analyses - Imaging Sub-Study

Descriptive analyses will be performed on the imaging sub-study data. These analyses will be exploratory and will investigate quantitative assessments of TR as well as right ventricular function. This data will be compared descriptively between MRI/CT and TTE at baseline and at follow-up.

1.5 Randomization

[Redacted]

1.6 Blinding

[Redacted]

2.0 ANALYSIS CONSIDERATIONS

2.1 Analysis Population

2.1.1 Randomized Cohort

The Intention-to-Treat, As-Treated, Per-Protocol and Attempted Procedure populations are defined below. For all the analysis, the duration of follow-up will be calculated from the date of the Treatment visit.

Statistical Analysis Plan

Intent-to-Treat (ITT) Population

[Redacted text]

[Redacted text]

Per-Protocol Population

[Redacted text]

Attempted Procedure (AP) Population

[Redacted text]

Statistical Analysis Plan

2.1.2 Single-Arm Cohort

Attempted Procedure Population

[REDACTED]

2.1.3 Imaging Sub-Study

Imaging Population

[REDACTED]

- [REDACTED]
- [REDACTED]
- [REDACTED]

2.1.4 Roll-In Cohort

Attempted Procedure Population

[REDACTED]

2.2 Statistical Methods

2.2.1 Descriptive Statistics for Continuous Variables

For continuous variables (e.g., age, 6MWT), results will be summarized with the number of observations, means, and standard deviations, and, in addition, with medians, quartiles, minimums, maximums, and 95% confidence intervals for the means, when specified.

2.2.2 Descriptive Statistics for Categorical Variables

For categorical variables (e.g. sex, TR Severity), results will be summarized with subject counts and percentages/rates, with exact 95% Clopper-Pearson¹ confidence intervals when specified. Differences between the two subgroups, when specified, will be summarized with the difference in percentages and the Newcombe² score 95% confidence interval for the difference of two percentages.

2.2.3 Survival Analyses

Survival analysis will be conducted to analyze time-to-event variables. Subjects without events will be censored at their last known event-free time point when they stay in the study. Survival curves will be

Statistical Analysis Plan

constructed using Kaplan-Meier estimates.

2.3 Endpoint Analysis

As the Coronavirus Disease 2019 (COVID-19) pandemic has spread around the globe, the following analysis mechanism will be implemented to minimize the potential confounding effect from this emerging infectious disease for the trial primary and secondary endpoints set forth in assessing the trial success and labeling claims. In alignment with the guidance documents by FDA and EU as follows, additional considerations were given to the impact of the COVID-19 pandemic on the primary and secondary endpoint analyses for this study:

- “Statistical Considerations for Clinical Trials During the COVID-19 Public Health Emergency – Guidance for Industry” published in June 2020
- “FDA Guidance on Conduct of Clinical Trials of Medical Products during the COVID-19 Public Health Emergency” updated on 03-June-2020
- EU “Guidance on the Management of Clinical Trials during the COVID-19 (Coronavirus) pandemic” updated on 28-April-2020

As such, prespecified methods are included in the sections that follow to indicate the handling of any outcomes impacted by COVID-19 as well as effects to minimize missing endpoint data COVID-19 pandemic. Unless otherwise specified, the impact of COVID-19 on the primary analysis of the primary and secondary endpoints of each cohort will be as follows:

For subjects who have experienced any hospitalization or death related to COVID-19 (relatedness adjudicated by CEC), all subsequent follow-up period for those subjects, after their first CEC adjudicated COVID-19 related hospitalization admission date or death event, will be censored. The first adjudicated COVID-19 related hospitalization or death event along with the subsequent follow-up data (KCCQ, 6MWT, MAE, hospitalizations, etc.) will not contribute towards any primary analysis for the primary or secondary endpoints analyses, except for the echo parameters (e.g. TR). Any subject who had a COVID-19 infection but did not experience a CEC-adjudicated COVID-19 related hospitalization or death will not be censored.

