**9 STATISTICAL CONSIDERATIONS**

The following section describes the statistical methods for the clinical investigation. Additional details on statistical analyses, including justification of clinical investigation design, impact of COVID-19 on the primary endpoint analysis, poolability analyses, subgroup analyses and analysis of descriptive endpoints, are provided in a separate Statistical Analysis Plan (SAP).

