2.11.1 Multiplicity – Randomized Cohort

The secondary endpoints for the Randomized Cohort will be evaluated for labeling claims if the primary endpoint is met. The secondary endpoints for the Randomized Cohort will be tested sequentially in the following order:

- Freedom from major adverse events (MAE) occurring after procedure attempt (femoral vein puncture) at 30 days.
- Change in KCCQ at 12 months over baseline (superiority of Device vs. Control)
- TR Reduction to moderate or less at 30 days post procedure (superiority of Device vs. Control)
- Change in 6MWT at 12 months over baseline (superiority of Device vs. Control)
- Recurrent HF hospitalizations at 24 months (superiority of Device vs. Control)
- Freedom from all-cause mortality, tricuspid valve surgery, and tricuspid valve intervention at 24 months (superiority of Device vs. Control)

The two secondary endpoints assessed at 24 months (recurrent HF hospitalizations and freedom from all-cause mortality, tricuspid valve surgery and tricuspid valve intervention) will be evaluated when all randomized subjects complete 24-month follow-up for additional labeling claims.

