2.12.3 COVID-19 Relatedness

To understand the impact of COVID-19 pandemic on the clinical outcomes, sensitivity analysis for the primary endpoint of the randomized and single-arm will be performed to include all the adjudicated events and follow-up periods for each endpoint regardless the status of COVID-19 infection.

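### The COVID-19 rule removes deaths from secondary endpoints named all-cause mortality and later data from the other non-echo secondaries, and the all-events sensitivity analysis covers only the two primary endpoints

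*SAP*

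**What the plan says.** SAP 2.3 sets a default for both cohorts: "Unless otherwise specified, the impact of COVID-19 on the primary analysis of the primary and secondary endpoints of each cohort" is handled by one rule. All follow-up of a subject "after their first CEC adjudicated COVID-19 related hospitalization admission date or death event, will be censored". The triggering event "will not contribute towards any primary analysis for the primary or secondary endpoints analyses". The same holds for what is recorded afterwards; the SAP's list of such data names KCCQ, 6MWT, MAE and hospitalizations. The one stated exemption is for echo measures. Infection without an adjudicated COVID-19 hospitalization or death triggers nothing.

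The rule reaches two endpoints named for all-cause mortality. One is last in the randomized testing order of SAP 2.11.1: "Freedom from all-cause mortality, tricuspid valve surgery, and tricuspid valve intervention at 24 months (superiority of Device vs. Control"). SAP 2.3.1.2.6 calls it a secondary measure of safety. The other is Single-arm freedom from all-cause mortality and tricuspid valve surgery at 12 months, tested against a 65% goal (SAP 2.3.2.2.5). Protocol Appendix II defines all-cause death with no exclusion by cause.

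The check is narrower than the rule. Under SAP 2.12.3, a "sensitivity analysis for the primary endpoint of the randomized and single-arm will be performed to include all the adjudicated events" and follow-up regardless of COVID-19 status. Protocol section 9 likewise refers the reader to the SAP for the "impact of COVID-19 on the primary endpoint analysis" and does not mention secondary endpoints there.

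**The concern.** The secondary endpoints of both cohorts are meant to support labelling claims (SAP 2.11.1 and 2.11.2). A survival claim worded as all-cause would rest on a count that leaves out some deaths. Observed 12-month KCCQ and 6MWT results of subjects who survived a COVID-19 admission would be set aside. HF hospitalizations after such an admission would not count, although Protocol 9.2.1.2.5 says that all follow-up available through 24 months enters that analysis.

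The trigger occurs after enrollment or randomization, and censoring at it is neutral only if the admission is unrelated to the subject's later risk. In a frail population that assumption should be tested. The SAP plans such a test for the primary endpoints but, on the visible text, not for the secondaries.

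**Working it through.** **1. Scope of the rule against scope of the check**

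| Endpoint | Rule in SAP 2.3 | All-events analysis in SAP 2.12.3 |
|---|---|---|
| Primary, both cohorts | applies | yes |
| 30-day MAE, both cohorts | applies (MAE is named) | no |
| Mortality/surgery(/intervention), both cohorts | applies | no |
| HF hospitalization, both cohorts | applies | no |
| 6MWT change, both cohorts; KCCQ change, randomized | applies | no |
| TR reduction, both cohorts | exempt (echo) | not needed |

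No visible text in the secondary endpoint sections overrides the default. The SAP contents list three subsections under 2.12. Two are titled for the randomized primary endpoint, and the third is 2.12.3.

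**2. Which stated figures can be rebuilt**

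The SAP gives power of about 80% for the 24-month endpoint (450 subjects), above 95% for randomized MAE (about 175) and about 83% for Single-arm survival (100). Their event rates are redacted, so they cannot be reproduced. The pilot MAE limit can: for 1 event in 85, the one-sided 95% Clopper-Pearson upper limit is 5.46%, which matches the stated 5.5%. No stated figure is disputed.

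The rest is illustrative. COVID-19 rates are an assumption, shown as 1 to 5 per 100 subjects. Exact binomial tests stand in for redacted methods, and a censored subject is treated as leaving the denominator.

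**3. Single-arm survival: n = 100, goal 65%, one-sided 2.5%**

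The criterion is a Clopper-Pearson lower 97.5% limit above 65%.
- 25 events in 100: limit 65.34%, passes.
- 26 events in 100: limit 64.27%, fails.
- 26 events of which one is an excluded COVID-19 death, leaving 25 in 99: limit 65.02%, passes.

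The most non-COVID events that still pass:

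| COVID-19 deaths | 1 | 2 | 3 | 5 |
|---|---|---|---|---|
| Deaths excluded | 25 | 24 | 24 | 23 |
| Deaths counted | 24 | 23 | 22 | 20 |

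Suppose the non-COVID event-free rate is 78%, which gives exact power of 80.3%. Counting COVID-19 deaths of 1, 2, 3 or 5% lowers the rate to 77, 76, 75 or 73% and the power to 73, 64, 55 or 37%.

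**4. The 24-month randomized endpoint: 225 per arm, two-sided 5%**

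With d the difference in event proportions and p̄ their mean, power = Φ{[d − 1.96√(2p̄(1−p̄)/225)] / √([p₁(1−p₁)+p₂(1−p₂)]/225)}. Assume 40% events on Control and 27.5% on Device. Then d = 0.125, p̄ = 0.3375, and power = Φ[(0.125 − 0.0874)/0.0442] = 80.3%. Power when COVID-19 deaths are counted:

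| COVID-19 deaths added (points) | 1 | 2 | 3 | 5 |
|---|---|---|---|---|
| Both arms equally | 79.7% | 79.2% | 78.7% | 77.9% |
| Device arm only | 73% | 65% | 56% | 38% |

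Balanced deaths cost about 0.5 to 2.5 points. One-sided imbalance is the extreme case.

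**5. Randomized 30-day MAE: n = 175, goal 90%, one-sided 2.5%**

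Nine events pass (limit 90.46%) and ten fail (89.74%). Ten with one excluded, 9 in 174, pass (90.41%). A reversal is unlikely, for two reasons.
- Window: if 1 to 5% of 175 subjects have a COVID-19 event spread evenly over 12 to 24 months, the number falling within 30 days is between 175 × 0.01 × 30/730 = 0.07 and 175 × 0.05 × 30/365 = 0.72. Only those that are, or are followed by, an MAE matter.
- Margin: under the exact test, power above 95% needs an MAE rate of at most about 3.1% (175 × 0.031 = 5.4 events). At that rate the chance of 10 or 11 events is about 4%. At the pilot's 1.2% it is below 0.01%.

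**The case against.** The rule is prespecified, cites regulatory guidance on trials during the pandemic, and has a stated aim: to keep a new infectious disease from confounding the device comparison. The MAE assumption rests on November 2018 data, so separating COVID-19 events from that benchmark is defensible. This stands, and the main analysis need not change.

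Redaction also limits certainty. The rule allows exceptions elsewhere, and parts of the secondary endpoint sections, the missing-data section and the opening of 2.12 are hidden. An override cannot be ruled out. If one exists, pointing to it would answer the affected part of this point.

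A reader might infer more than the documents support:
- That affected subjects are deleted. They are censored: events and follow-up before the COVID-19 hospitalization or death still count.
- That nobody would see the effect. SAP 3.2 summarizes adjudicated events by treatment group and tabulates COVID-19-related events, and SAP 3.3 reports early termination, including death, by group. The burden is visible. What is missing is a re-test of the secondaries.
- That the arms differ in hospital exposure and the bias therefore favours one of them. The documents give no such comparison, and the single-group tests have no comparison arm.
- That the MAE result could easily be reversed. The 30-day window and the planned margin make this improbable.
- That the primary Finkelstein-Schoenfeld result goes unchecked. SAP 2.12.3 covers it.

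**Conclusion.** The point holds on the visible text. Two endpoints named all-cause mortality leave out deaths that the protocol's definition counts. The other non-echo secondaries lose all data after a COVID-19 admission, and the planned all-events analysis does not extend to any of them.

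The size cannot be fixed from the documents, because they give neither COVID-19 rates nor the design event rates for the affected endpoints. Under the assumed 1 to 5%, one excluded death can change the Single-arm survival conclusion when the count is at the boundary. The 24-month comparison is sensitive if COVID-19 deaths are unbalanced and nearly insensitive if they are balanced. The effect on 30-day MAE is likely small. These results rest on exact binomial and two-proportion approximations. The direction of any bias is unknown. This is a gap in sensitivity analysis and labelling, and it does not show that any claim would be wrong.

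**What to change.** Extend SAP 2.12.3 to the non-echo secondary endpoints of both cohorts: 30-day MAE, the mortality/surgery/intervention endpoints, HF hospitalization, 6MWT change and the randomized KCCQ change. Use all adjudicated events and follow-up regardless of COVID-19 and report each result beside the main one. TR reduction needs no rerun.

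Label the main versions of the two mortality endpoints as excluding COVID-19-related deaths and follow-up after a COVID-19 admission.

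Keep the added analyses non-gating. Requiring the same conclusion in both would add a second success criterion inside the fixed testing sequence and cost power, and the gap does not call for that.

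The cost is SAP wording and a few reruns of methods already planned. The downside for the sponsor is that a labelling claim may be shown to be sensitive to COVID-19 events.

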2.3.1 Randomized Cohort

2.3.1.1 Randomized Cohort – Primary Endpoint

The primary endpoint for the randomized study is a hierarchical composite of all-cause mortality or tricuspid valve surgery, heart failure (HF) hospitalizations, and quality of life improvement assessed using

Statistical Analysis Plan

the Kansas City Cardiomyopathy Questionnaire (KCCQ) at 12 months. The endpoint will be compared between the Device group and the Control group in a hierarchical fashion using the Finkelstein-Schoenfeld³ methodology as follows:

- Time to all-cause death or tricuspid valve surgery
- Number of HF hospitalizations
- Improvement of ≥ 15 points in KCCQ from baseline

The null and alternative hypotheses are stated as:

H_0 : None of the components are different between the Treatment and Control group

H_1 : At least one components are different between the Treatment and Control group

The primary endpoint will be analyzed using the Finkelstein-Schoenfeld method and the null hypothesis will be rejected at a two-sided 5% level of significance.

The primary analysis for the primary endpoint will be performed on the ITT population. [REDACTED]

[REDACTED]

[REDACTED]

[REDACTED]

[REDACTED]

Statistical Analysis Plan

[REDACTED]

[REDACTED]

$$T = \sum_{i=1}^n U_i D_i$$

[REDACTED]

$$U_i = \sum_{i \neq j} u_{ij}$$

[REDACTED]

$$V = \frac{n_D(n - n_D)}{n(n-1)} \sum_{i=1}^n U_i^2$$

[REDACTED]

[REDACTED]

[REDACTED]

[REDACTED]

[REDACTED]

[REDACTED]

[REDACTED]

[REDACTED]

[REDACTED]

[REDACTED]

[REDACTED]

Statistical Analysis Plan

[REDACTED]

2.3.1.2 Randomized Cohort – Secondary Endpoints

The following six secondary endpoints will be used as secondary measures of safety and effectiveness for the TriClip™ system. The secondary endpoints will be tested at a two-sided 5% level of significance unless otherwise specified. The primary analysis population of the secondary endpoints will be the ITT population. Additional analyses may be performed on the PP and AT populations.

2.3.1.2.1 TR Reduction to Moderate or Less at 30-Day Visit

Subjects in the randomized Device group are expected to experience greater reduction in TR severity than subjects in the Control group. The null and alternative hypotheses are stated as:

$$H_0: P_{D,TR \leq 2} - P_{C,TR \leq 2} = 0 \text{ vs.}$$

$$H_1: P_{D,TR \leq 2} - P_{C,TR \leq 2} \neq 0$$

where $P_{D,TR \leq 2}$ and $P_{C,TR \leq 2}$ represent the proportion of subjects with TR reduced to moderate or less at 30-day visit in the Device and Control groups respectively. [REDACTED]

[REDACTED]

[REDACTED] The null hypothesis will be rejected at a two-sided 5% level of significance.

